12.7.2. Collection of Pregnancy Information

- Investigator will collect pregnancy information on any female subject, who becomes pregnant while participating in this study.
- Information will be recorded on the appropriate form and submitted to GSK within 2 weeks of learning of a subject's pregnancy.
- Subject will be followed to determine the outcome of the pregnancy. The investigator will collect follow-up information on mother and infant, which will be forwarded to GSK. Generally, follow-up will not be required for longer than 6 to 8 weeks beyond the estimated delivery date.
- Any termination of pregnancy will be reported, regardless of fetal status (presence or absence of anomalies) or indication for procedure.
- While pregnancy itself is not considered to be an AE or SAE, any pregnancy complication or elective termination of a pregnancy will be reported as an AE or SAE.
- A spontaneous abortion is always considered to be an SAE and will be reported as such.
- Any SAE occurring as a result of a post study pregnancy which is considered reasonably related to the study treatment by the investigator will be reported to GSK as described in [Appendix 5](#). While the investigator is not obligated to actively seek this information in former study participants, he or she may learn of an SAE through spontaneous reporting.

Any female subject who becomes pregnant while participating:

- Will be withdrawn from the study.
- The investigator will attempt to collect pregnancy information on any female partner of a male study subject who becomes pregnant while participating in this study. This applies only to subjects who are randomized to receive study medication.
- After obtaining the necessary signed informed consent from the female partner directly, the investigator will record pregnancy information on the appropriate form and submit it to GSK within 2 weeks of learning of the partner's pregnancy.
- The partner will also be followed to determine the outcome of the pregnancy. Information on the status of the mother and child will be forwarded to GSK.

- Generally, follow-up will be no longer than 6 to 8 weeks following the estimated delivery date. Any termination of the pregnancy will be reported regardless of fetal status (presence or absence of anomalies) or indication for procedure.

12.8. Appendix 8: Follow-up for Gastrointestinal Findings

Subjects who experience diarrhoea or enteritis should be evaluated with additional fecal occult blood tests and stool cultures as deemed appropriate by the investigator. Any subject with a positive fecal occult blood test should be referred to a gastroenterologist for further evaluation at the discretion of the investigator.

Subjects who experience an AE of diarrhoea or enteritis should have additional fecal occult blood testing, as well as a routine stool culture performed, which may include the recovery of pathogenic bacteria such as *Salmonella*, *Shigella*, *Campylobacter*, *Yersinia*, *Vibrio*, *Staphylococcus aureus*, *Escherichia coli* 0157, and enterohemorrhagic *Escherichia coli*.

In addition, if the subject meets the clinical criteria outlined in [Appendix 9](#), *Clostridium difficile* toxin detection should be conducted.

Note: Additional testing is at the discretion of the investigator if it is believed the GI signs/symptoms are due to cholinergic effects and/or if the GI signs/symptoms occur within 24 hours of the infusion.

12.9. Appendix 9: *Clostridium Difficile* Testing Procedure and Algorithm

Signs/Symptoms indicate possible GI disturbance **and**

[figure not shown]
Subject has ≥ 3 non-formed stool specimens in a 24 hour period or a significant change from baseline

Collect specimen in a sterile container (no preservative)

Transport to local lab at 2-8°C*

Local lab performs testing or sends to a reference lab (if according to their procedures**)

Freeze remaining portion of sample and save for further testing (if necessary)

*If processing and testing cannot be performed within 24 hours, the specimen should be frozen immediately after collection.

**If specimen is sent to a reference laboratory, the procedures to be ordered should follow the same algorithm above.

GDH = glutamate dehydrogenase; NAAT = nucleic acid amplification test

12.10. Appendix 10: Country-Specific Requirements

No country-specific requirements exist.

12.11. Appendix 11: Physiologically Based Pharmacokinetic Model Input Parameters

Parameters	Value	References /Resources
Molecular weight	448.5	Investigator Brochure
Compound type	Dibasic	Technical Evidence Document
pKa 1	8.83	Adamantis
pKa 2	6.2	Calculated using Adamantis
cLog P	0.16	Calculated using Adamantis
Fu Plasma	0.67	Study # GlaxoSmithKline Document Number 2013N170240_00
Blood:Plasma ratio	0.95	Study # GlaxoSmithKline Document Number 2012N131922_00
Vdss	1.30	Predicted Full PBPK with additional organ compartment and Kp scalar 0.7
Additional organ Kp	100	Predicted value of pigmented tissue from QWBA Study # GlaxoSmithKline Document Number 2012N156820_00
CYP3A4 f _m	0.25	
CYP3A4 CL _{int} (μL/min/pmol P450)	0.0434	SimCYP calculation based on CL _{i.v.} of 43 L/hr with measured renal clearance of 16 L/hr with CYP3A4 f _m = 0.25
Additional HLM CL _{int} (μL/min/mg protein)	9.00	SimCYP calculation based on CL _{i.v.} of 43 L/hr with measured renal clearance of 16 L/hr with CYP3A4 f _m =0.25

CYP = cytochrome 450, Fu = fraction unbound; Vdss = volume of distribution at steady state; Kp = equilibrium partition coefficient of drug; PBPK = physiologically based pharmacokinetic model; QWBA = quantitative whole-body autoradioluminography

## 1. REPORTING & ANALYSIS PLAN SYNOPSIS

Overview	Key Elements of the RAP
Purpose	
The purpose of this reporting and analysis plan (RAP) is to describe:
 
 
Any planned analyses and output to be included in the clinical study report for Protocol BTZ116849.
 

Protocol	
 
This RAP is based on the original protocol (Dated: 01-MAR-2016) of study BTZ116849 (GSK Document No. : 2014N209329_00).
 

Primary Objective	
 
To compare the pharmacokinetics of gepotidacin administered as a 750 mg IV dose in normal healthy subjects compared with subjects with mild, moderate, and severe renal impairment, and with subjects with end stage renal disease (ESRD).
 

Primary Endpoint	
 
Plasma primary PK endpoints include AUC(0-∞) and Cmax of gepotidacin, as data permit
 
Urine primary PK end points include Ae total, fe%, and CLr of gepotidacin, as data permit
 
Dialysate primary PK end points include AUC(t0-t1), CLD, and Frem%(0-4), of gepotidacin, as data permit
 

Study Design	
 
This is a Phase I, nonrandomized, open-label, parallel-group, multi-center, multi-part study that will evaluate the pharmacokinetics, safety, and tolerability of a single IV dose of gepotidacin 750 mg over 2 hours in subjects with normal renal function; subjects with mild, moderate, and severe renal impairment; and subjects with end-stage renal disease (ESRD; on dialysis and not on dialysis).
 

Planned Analyses	
 
Safety and PK data will be presented in tabular and/or graphical format and summarized descriptively according to GSK's Integrated Data Standards Library (IDSL) standards.
 

Analysis Populations	
 
Safety Population – defined as all subjects who receive at least 1 dose of study drug and have at least one postdose safety assessment.
 
Pharmacokinetic Population - defined as all subjects who received at least 1 dose of gepotidacin and have evaluable PK data for gepotidacin.
 
Pharmacokinetic Parameter Population - defined as all subjects in the PK Population, for whom valid and evaluable PK parameters were derived. This population will be used in the assessment and characterization of PK parameters.
 

Hypothesis	
 
A formal hypothesis will not be tested; however, an estimation approach will be taken to characterize the PK of gepotidacin in subjects with mild, moderate, severe renal impairment and in subjects with ESRD (on dialysis and not on dialysis) compared with matched subjects with normal renal function.
 

## 2. SUMMARY OF KEY PROTOCOL INFORMATION

### 2.1. Changes to the Protocol Defined Statistical Analysis Plan

There were no changes or deviations to the originally planned statistical analysis specified in the protocol (Dated: 01-MAR-2016).

### 2.2. Study Objective(s) and Endpoint(s)

Objectives	Endpoints
Primary Objectives	Primary Endpoints

 
To compare the PK of gepotidacin administered as a 750 mg IV dose in normal healthy subjects compared with subjects with mild, moderate, and severe renal impairment, and with subjects with ESRD.
 
	
 
Plasma primary PK endpoints include AUC(0-∞) and Cmax of gepotidacin, as data permit
 
Urine primary PK end points include Ae total, AUC(t0-t1), fe%, and CLr of gepotidacin, as data permit
 
Dialysate primary PK end points include AUC(t0-t1), CLD, and Frem%(0-4), of gepotidacin, as data permit
 

Secondary Objectives	Secondary Endpoints

 
To assess the safety and tolerability of gepotidacin administered as a 750-mg IV dose in normal healthy subjects compared with subjects with mild, moderate, severe renal impairment, and with subjects with ESRD
 
	
 
12-lead safety electrocardiogram readings, change from baseline in vital sign measurements (blood pressure and heart rate), monitoring of adverse events, toxicity grading of clinical laboratory test results, and physical examinations
 

 
To evaluate the secondary PK parameters of gepotidacin administered as a 750-mg IV dose in normal healthy subjects compared with subjects with mild, moderate, and severe renal impairment, and with subjects with ESRD
 
	
 
Plasma PK endpoints include AUC(0-t), CL, λz, t1/2, Tmax, Vss, and Vz, as data permit
 
Urine PK endpoint includes Ae(t1-t2) and AUC(0-t) as data permit
 
Dialysate PK endpoints include Arem(0-1), Arem(1-2), Arem(2-3), Arem(3-4), and Arem(0-4), as data permit
 

Exploratory Objectives	Exploratory Endpoints

 
To evaluate the saliva pharmacokinetics of gepotidacin (subjects in Part 1 only).
 
	
 
Primary saliva PK endpoints include AUC(0-∞) and Cmax of gepotidacin, as data permit
 
Secondary saliva PK endpoints include AUC(0-t), CL, λz, t1/2, Tmax, Vss, Vz, RAUC(0-t) and RAUC(0-∞) as data permit
 

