This will be a multi-part study, in which pharmacokinetic (PK) requirements must be met (observed mean values: area under the curve [AUC] <48 $\mu\text{g}\cdot\text{hr}/\text{mL}$ and maximum observed concentration [Cmax] <14 $\mu\text{g}/\text{mL}$); and safety and tolerability will be reviewed before enrolling subjects into the next part of the study. In Part 1, subjects with normal renal function; subjects with moderate renal impairment; and subjects with severe renal impairment and subjects with ESRD not on hemodialysis will be enrolled. In Part 2 (optional), subjects with normal renal function, subjects with mild renal impairment, and subjects with ESRD on hemodialysis will be enrolled based on the PK, safety, and tolerability data of Part 1. Subjects with mild renal impairment may be studied if there is a significant difference in PK between subjects with moderate and severe renal impairment compared to subjects with normal renal function and modelling cannot accurately predict PK in subjects with mild renal impairment. Subjects with ESRD on hemodialysis will be studied provided that the PK requirements are met (observed mean values in subjects with severe impairment do not exceed the threshold: area under the curve [AUC] <48 $\mu\text{g}\cdot\text{hr}/\text{mL}$ and maximum observed concentration [Cmax] <14 $\mu\text{g}/\text{mL}$). The dose may be adjusted for subjects with ESRD on hemodialysis if either PK parameter is predicted to exceed the threshold. See the study schematic in Figure 1 for more details.

For subjects with normal renal function, subjects with mild, moderate, and severe renal impairment, and subjects with ESRD not on dialysis: subjects will participate in 1 treatment period and blood and urine samples will be collected for PK analysis of gepotidacin concentrations according to the Time and Events Tables (Table 2 and Table 3). In addition, saliva samples (subjects in Part 1 only) will be collected for the PK analysis of gepotidacin concentrations according to the Time and Events Tables (Table 2 and Table 3). Blood, urine, and saliva samples will be collected up to approximately 48 hours after dosing.

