Saliva collection for pharmacokinetics ^c			X	X	X		See Table 3 for time points.
AE/SAE review	X	X	←-----→			X	
Concomitant medication review		X	←-----→			X	

AE = adverse event, Clcr = estimated creatinine clearance; eGFR = estimated glomerular filtration rate, ECG = electrocardiogram, FSH = follicle stimulating hormone; HIV = human immunodeficiency virus; PGx = pharmacogenetic, SAE = serious AE; WCBP = women of childbearing potential.

- a If test has otherwise been performed within 3 months before the first dose of study treatment, testing at Screening is not required.
- b Informed consent for optional substudies (e.g., genetics research) must be obtained before collecting a sample.
- c Subjects in Part 1 only. It should be noted that subjects with renal impairment may be on medications that may prevent saliva collections.

Table 3 Safety and PK Assessments (Groups A, B, C, D, and E)

Procedure ^a	Predose	Treatment Period Time point (hours)														
		0	0.25	0.5	1	1.5	2	2.5	3	4	6	8	12	24 ^b	36 ^b	48 ^b
12-lead electrocardiogram	X					X	X			X		X	X	X	X	X
Vital signs	X					X	X			X		X	X	X	X	X
Treatment administration 2-hour IV gepotidacin infusion		X														
Blood collection for pharmacokinetics	X		X	X	X	X	X	X	X	X	X	X	X	X	X	X
Urine collection for pharmacokinetics (subjects with normal renal function) ^c	X	X					X			X	X	X	X	X	X	
Urine collection for pharmacokinetics (subjects with renal impairment) ^d	X	X								X		X	X	X	X	
Saliva collections ^e	X		X	X	X	X	X	X	X	X	X	X	X	X	X	X

^a When coinciding with safety and/or pharmacokinetic assessments, electrocardiograms, vital signs, and pharmacokinetic blood collections should be performed in said order.

^b The 24-, 36-, and 48-hour postdose time points correspond to time points on Day 2 and 3, respectively.

^c Urine collection intervals for subjects with normal renal function (Group A and Group D) include 0 (pre-dose), 0 to 2 hours, 2 to 4 hours, 4 to 6 hours, 6 to 8 hours, 8 to 12 hours, 12 to 24 hours, 24 to 36 hours, and 36 to 48 hours.

^d Urine collection intervals for subjects with renal impairment (Group B, Group C, and Group E) include 0 hour (pre-dose), 0 to 6 hours, 6 to 12 hours, 12 to 24 hours, 24 to 36, and 36 to 48 hours.

^e Subjects in Part 1 only. It should be noted that subjects with renal impairment may be on medications that may prevent saliva collections.

Table 4 Time and Events Tables (Group F)

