**Table 7 Derived Saliva Pharmacokinetic Parameters (subjects in Part 1 only)**

Parameter	Parameter Description
AUC(0-t)	Area under the concentration-time curve from time 0 (predose) to time of last quantifiable concentration, to be calculated using the linear trapezoidal rule for each incremental trapezoid and the log trapezoidal rule for each decremental trapezoid.
AUC(0-∞)	Area under the concentration-time curve from time 0 (predose) extrapolated to infinite time, calculated as: $AUC = AUC(0-t) + C(t) / \lambda z$
%AUCex	The percentage of AUC (0-∞) obtained by extrapolation (%AUCex) will be calculated as: $[AUC(0-inf) - AUC(0-t)] / AUC(0-inf) \times 100$
Cmax	Maximum observed concentration, determined directly from the concentration-time data.
Tmax	Time to first occurrence of Cmax
t1/2	Terminal phase half-life will be calculated as: $t_{1/2} = \ln 2 / \lambda z$
λz	Terminal-phase rate constant
CL	Systemic clearance, calculated as: $CL = \text{Dose} / AUC(0-inf)$
Vss	Volume of distribution at steady-state of parent drug, calculated as: $V_{ss} = MRT(0-inf) * (CL)$
Vz	Volume of distribution of the terminal phase, calculated as: $V_z = \text{Dose} / (AUC(0-inf) * \lambda z)$
RAUC(0-t)	The ratio of the AUC(0-t) observed in saliva relative to the AUC(0-t) in plasma, calculated as: $RAUC(0-t) = AUC(0-t) \text{ saliva} / AUC(0-t) \text{ plasma}$
RAUC(0-∞)	The ratio of the AUC(0-∞) observed in saliva relative to the AUC(0-∞) in plasma, calculated as: $RAUC(0-\infty) = AUC(0-\infty) \text{ saliva} / AUC(0-\infty) \text{ plasma}$

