**Safety and PK Assessments (Groups A, B, C, D, and E)**

Procedure a	Predose	Treatment Period Time point (hours)														
		0	0.25	0.5	1	1.5	2	2.5	3	4	6	8	12	24 b	36 b	48 b
12-lead electrocardiogram	X					X	X			X		X	X	X	X	X
Vital signs	X					X	X			X		X	X	X	X	X
Treatment administration 2-hour IV gepotidacin infusion		X														
Blood collection for pharmacokinetics	X		X	X	X	X	X	X	X	X	X	X	X	X	X	X
Urine collection for pharmacokinetics (subjects with normal renal function) c	X	X					X			X	X	X	X	X	X	
Urine collection for pharmacokinetics (subjects with renal impairment) d	X	X								X		X	X	X	X	
Saliva collections e	X		X	X	X	X	X	X	X	X	X	X	X	X	X	X

- a When coinciding with safety and/or pharmacokinetic assessments, electrocardiograms, vital signs, and pharmacokinetic blood collections should be performed in said order.
- b The 24-, 36-, and 48-hour postdose time points correspond to time points on Day 2 and 3, respectively.
- c Urine collection intervals for subjects with normal renal function (Group A and Group D) include 0 (pre-dose), 0 to 2 hours, 2 to 4 hours, 4 to 6 hours, 6 to 8 hours, 8 to 12 hours, 12 to 24 hours, 24 to 36 hours, and 36 to 48 hours.
- d Urine collection intervals for subjects with renal impairment (Group B, Group C, and Group E) include 0 hour (pre-dose), 0 to 6 hours, 6 to 12 hours, 12 to 24 hours, 24 to 36, and 36 to 48 hours.
- e Subjects in Part 1 only. It should be noted that subjects with renal impairment may be on medications that may prevent saliva collections.

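### RAUC(0-t) divides a saliva area and a plasma area that may end at different times, so the ratio is off whenever the two last quantifiable times differ

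*SAP*

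**What the plan says.** SAP section 2.2 lists, among the secondary saliva endpoints of the exploratory objective, "Tmax, Vss, Vz, RAUC(0-t) and RAUC(0-∞) as data permit". The protocol's endpoint table does not contain the two ratios. They are defined in SAP Table 7 (section 7.1.3.1). RAUC(0-t) is "The ratio of the AUC(0-t) observed in saliva relative to the AUC(0-t) in plasma", and the companion RAUC(0-∞) is "The ratio of the AUC(0-∞) observed in saliva relative to the AUC(0-∞) in plasma".

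Table 7 describes saliva AUC(0-t) as "Area under the concentration-time curve from time 0 (predose) to time of last quantifiable concentration". SAP Table 4 describes plasma AUC(0-t) in the same terms, so t belongs to each matrix separately. Both areas use the "linear trapezoidal rule for each incremental trapezoid and the log trapezoidal rule for each decremental trapezoid".

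The nominal schedule is shared: "Blood, urine, and saliva samples will be collected up to approximately 48 hours after dosing" (Protocol 4.1). Footnote e to Protocol Table 3, repeated in SAP Appendix 1, adds: "It should be noted that subjects with renal impairment may be on medications that may prevent saliva collections".

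SAP Table 3.8 summarises both ratios by renal function for Part 1. SAP 7.1.3.2 and Protocol 9.4.3.1 also set log saliva AUC(0-t) against log plasma AUC(0-t).

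**The concern.** A ratio of two areas measures relative exposure only if both areas cover the same interval. Here they do so only when the last quantifiable times agree. The shared 48-hour schedule fixes when samples are planned, not when each matrix stops being quantifiable or when a saliva sample is missed. Neither document sets a common t, a minimum overlap or a rule for unequal last times.

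At stake is how Table 3.8 and the saliva-plasma AUC(0-t) plot are read. A difference in where the curves were cut could be taken for a difference in how the drug partitions into saliva. The summary is by renal group, and both elimination and last quantifiable time may differ by group, so the error may differ too.

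**Working it through.** The plan states no figure for RAUC, so there is none to reproduce.

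**Direction, without a PK model.** Let saliva = R × plasma at all times, with last quantifiable times ts (saliva) and tp (plasma). Then

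RAUC(0-t) / R = AUC(0-ts) / AUC(0-tp),

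where both areas on the right are plasma areas. This is below 1 if ts < tp, above 1 if ts > tp, and equal to 1 if ts = tp. With both areas cut at min(ts, tp), the result is exactly R.

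**Inputs for an illustration of size.**
- Dose 750 mg over 2 h; sampling times from Protocol Table 3; linear-up/log-down areas from SAP Tables 4 and 7.
- CL, normal: 43 L/h (Protocol Appendix 11).
- CL, severe: 750/28.9 = 25.95 L/h (Protocol Table 1, treating its AUC(0-t) as total AUC).
- V, assumed: 91 L, reading the unitless Vdss of 1.30 in Appendix 11 as L/kg × 70 kg; and 65 L, which gives a severe Cmax of 7.95 µg/mL against 7.93 in Table 1.
- One compartment, constant R. Plasma area taken to 48 h; stopping plasma at 24 h hardly matters (severe, V = 91 L: 24.3, 13.7 and 4.3%).

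**Example, severe, V = 91 L, last saliva value at 8 h.** AUC(0-8) = 24.892 and AUC(0-48) = 28.871 µg·h/mL. 24.892/28.871 = 0.862, so the ratio is 13.8% low. Normal: 16.741/17.403 = 0.962, so 3.8% low.

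Shortfall in RAUC(0-t):

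| Last saliva value | Normal, V 65 L | Normal, V 91 L | Severe, V 65 L | Severe, V 91 L |
|---|---|---|---|---|
| 6 h | 4.0% | 9.8% | 14.0% | 24.4% |
| 8 h | 1.1% | 3.8% | 6.3% | 13.8% |
| 12 h | 0.1% | 0.6% | 1.3% | 4.4% |

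**Loss driven by the assay.** Both matrices were cut at an equal assumed quantification limit (0.01, 0.05 or 0.1 µg/mL), with true ratio 0.1, 0.3, 0.5 or 1, giving 12 cases at V = 91 L:
- The severe group has 0% error in 7 of the 12, and at most -9.8%.
- In 6 cases both groups have 0%. In 4 the error is larger in severe, and in 2 it is larger in normal. At limit 0.1 and ratio 0.1 it is -22.2% in normal and -9.8% in severe; at limit 0.01 and ratio 0.3 it is 0% and -4.3%.

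**Reverse direction.** With true ratio 2, limit 0.05 and normal subjects at V = 91 L, plasma is last quantifiable at 8 h and saliva at 12 h. The ratio is 17.303/16.741 = 1.034 times the true value, or 3.4% high.

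**The case against.** The strongest reply concedes the definition and disputes the consequences.

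- *Footnote e does not describe early loss.* It says medications may prevent saliva collection. Protocol 6.11.1 asks for stable chronic medication from 7 days before dosing to Follow-up, so a drug that prevents saliva would plausibly do so at every time point. That leaves a missing ratio, which the as-data-permit wording covers. This stands.
- *A reader might infer that a constant ratio will appear to fall with renal impairment.* The table above shows that gradient only because it imposes the same saliva cut-off on both groups. Where the assay limit decides the cut-off, the share of area lost after concentration C is (C·V/CL)/(Dose/CL) = C·V/Dose, which does not depend on clearance. What remains comes from the sampling grid and has no fixed sign. The documents do not support a predicted decline.
- *A reader might quote far larger errors.* A shortfall of 30 to 40% at 8 h in severe impairment needs V of 150 to 200 L. That implies a Cmax of 4.2 to 3.3 µg/mL against 7.93 in Protocol Table 1. Even the 24% at 6 h is hard to reach through the assay: modelled plasma at 8 h is 1.13 µg/mL, so at a limit of 0.05 the true ratio would have to be below 0.05/1.13 = 0.044.
- *The mismatch is partly visible.* SAP 9.3.3 lists tlast and %AUCex for both matrices, and RAUC(0-∞) stands beside RAUC(0-t). This stands in part. A reader could see unequal windows but could not recover the right ratio from the summary table. RAUC(0-∞) also needs a terminal slope in both matrices, which is least likely to be available when saliva stops early, and no %AUCex limit is set.
- *The stakes are low.* No hypothesis, gate or dosing decision uses this ratio. This stands.

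**Conclusion.** The concern holds as a flaw of definition. As written, RAUC(0-t) gives a wrong ratio whenever the two last quantifiable times differ, low or high according to which matrix stops first. That follows from SAP Tables 4 and 7 and needs only a constant saliva-to-plasma ratio.

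The size is conditional, and the working figures are illustrations, not predictions. They rest on one compartment, an assumed V of 65 to 91 L and imposed cut-offs. Terminal half-life, quantification limits and the true ratio are absent from the documents, and the error is zero if the last times coincide. Loss of saliva samples in impaired subjects is foreseen as possible, not as early or expected. Bias may therefore differ between renal groups, but neither document establishes in which direction.

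The effect is confined to a secondary parameter of an exploratory objective and to the AUC(0-t) part of the saliva-plasma comparison. It is a minor point, worth correcting because a better definition is readily available.

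**What to change.** In SAP Table 7, define RAUC(0-t) per subject with both areas taken from 0 to the earlier of that subject's saliva and plasma last quantifiable times, and list that common time with the ratio. Use the same common-window pair in the saliva-plasma AUC(0-t) analysis of SAP 7.1.3.2. Leave RAUC(0-∞), and AUC(0-t) as a parameter within each matrix, as they are.

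The cost is a line in Table 7, a matching note in 7.1.3.2 and a partial-area setting in the noncompartmental software; no new data are needed. There is a small price in interpretation. The window will vary between subjects, and the ratio then describes only the shared interval, so it recovers the overall ratio only if partitioning is constant over time. The listed common time lets a reader judge this.
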